7.2 Missing data

Missing data will not be imputed. All analysis will be conducted based on the observed data. Any participants who attend a study visit but do not complete the simulated injection will be excluded from the analysis. Partial completion of the mSQAAQ will be analyzed per the instrument instructions.

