## 10.3 Data Management & Statistical Analysis

### 10.3.1 Data Analysis

A descriptive analysis will be conducted to assess the ease of use and confidence of use of the lebrikizumab pen. All participants having given an informed consent will be included in the analysis population.

The main endpoint of the study will be assessed via the mSQAAQ. The primary outcome reported from each individual question will be the proportion of participants responding “agreed” or “strongly agreed” to the question. Participants who do not complete an individual item in the mSQAAQ will have their remaining questions analyzed per instrument instructions.

Collected demographic information and health literacy level of study participants will be presented for the total analysis population as well as any selected sub-populations. A descriptive analysis of any AEs and/or product complaints reported during the study will be included for the total analysis population.

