### **10.5 Handling of Missing Data**

Any participants who attend a study visit but do not complete the simulated injection and mSQAAQ [9.10](#) will be excluded from the analysis. Partial completion of the mSQAAQ will be analyzed per the instrument instructions.

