5.2 All Patients Enrolled Set [ENR]

All Patients Enrolled (ENR) set will contain all patients who provide informed consent for this study.

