7. STATISTICAL CONSIDERATIONS

7.1 Statistical Tests and Confidence Intervals

Continuous variables will be summarized using descriptive statistics, i.e., by the number of non-missing and missing observations, mean, standard deviation (SD), first quartile (Q1), median, third quartile (Q3), minimum, and maximum.

Categorical variables will be summarized by frequency counts (n) and percentages (%). Percentages will not include the missing category and are calculated over the number of patients with available (non-missing) data. Counts of missing data will be provided in the tables for information only.

For reporting conventions, percentages will be reported to 1 decimal place unless greater precision is deemed appropriate, except for cases when 100% is presented. In cases of a count of 0, the percentage will not be presented. The 95% confidence interval (CI) for the response rates will be calculated using Clopper-Pearson method.

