10. DEMOGRAPHIC AND OTHER PATIENT CHARACTERISTICS

Demographic data and patient characteristics will be presented for the ENR. No statistical testing will be carried out for demographic or patient characteristics. The following demographic characteristics will be presented as described in [Section 7.1](#):

- Age at enrollment (years)
- Sex (Male, Female)
- Race (American Indian or Alaska Native, Asian, Black or African American, Native Hawaiian or Pacific Islander, White, Other, Multiple, Refused to answer)
- Ethnicity (Hispanic, Non-hispanic)
- Education (Less than High School, Completed High School/GED, Some College/Technical School, Graduated College/Technical School or more, refused to answer)
- Employment status (Employed Full-Time, Employed Part-Time, Unemployed, Student, Retired, Other, refused to answer)
- Total annual household income (\$0 to \$14,999, \$15,000 to \$24,999, \$25,000 to \$34,999, \$35,000 to \$44,999, \$45,000 to \$64,999, \$65,000 to \$74,999, \$75,000 or more, refused to answer)

A listing will also be provided for the above demographic characteristics.

Descriptive statistics (see [Section 7.1](#)) will be provided for the following patient characteristics:

Injection Experience:

- Number of subjects with any previous injection experience (Yes, No)
- Number and percentage of injection tool used (pre-filled syringe (PFS), Vial/Syringe, Other)

- Number and percentage of previous injection experience (Perform injections frequently on self, perform injections frequently on others, perform injections rarely on self, perform injections rarely on others)

A listing of injection experience will be provided for each term as collected in the eCRF, including the data listed above, the drug and/or device used for injection, and the last time they performed an injection.

Pregnancy:

- Number and percentage of participants who are individuals not of childbearing potential (INOCBP) (Yes, No)
- Number and percentage of Reason for being INOCBP (Surgically sterilized, Tubal Ligation, not capable of producing ova or embryo due to congenital anomaly)
- Number and percentage of pregnancy test completed (Yes, No)
 - Number and percentage of reason for pregnancy test not performed (Refused, unable to urinate, other)
 - Participants who read Instructions for Use (Yes, No)
 - Participant given the opportunity to have their questions about the injection simulation process answered (Yes, No)

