14.1.2 Analysis of Primary Variables

The primary analysis will be performed on the ENR. Each element will be summarized using descriptive statistics (see [Section 7.1](#)).

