15. SAFETY OUTCOMES

All outputs for safety outcomes will be based on the ENR. AE/SAE/Product complaints will be coded using the latest version of MedDRA at the time of data analysis. The MedDRA version used for a given output will be added in the footnote.

A listing by patient including each verbatim term, preferred term, start and end date, ongoing status (Yes/No), action taken, outcome, severity, seriousness, relationship to the device, and relationship to drug will also be provided.

A listing of adverse events, medications and product complaints will be provided. It will include patient responses to whether the participant experienced any adverse events during this study, whether the participant is currently taking any medication or therapy, whether the participant identified any product complaints, and whether a product complaint form was submitted to the study sponsor.

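### SAP 7.2 drops attendees who do not complete the simulated injection, against the all-consented set named for the primary analysis; its only possible effect on the primary proportion is to discard answers that were given

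*SAP*

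**What the plan says.** **Who is in the primary analysis.** SAP 5.2 says that the enrolled set (ENR) "set will contain all patients who provide informed consent for this study". SAP 14.1.2 adds: "The primary analysis will be performed on the ENR". Protocol 10.3.1 agrees: "All participants having given an informed consent will be included in the analysis population". Consent is the only condition in all three places.

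**Who is taken out.** SAP 7.2, under the missing-data heading, says: "Any participants who attend a study visit but do not complete the simulated injection will be excluded from the analysis". Protocol 10.5 has a related rule with a different condition. It starts "Any participants who attend a study visit but do not complete the simulated injection and mSQAAQ" and removes those participants from the analysis. The SAP rule names only the injection. SAP 3.3 nevertheless declares no changes from the protocol.

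**How percentages are formed.** SAP 7.1: "Percentages will not include the missing category and are calculated over the number of patients with available (non-missing) data". SAP 7.2 rules out imputation, and SAP 7.1 specifies Clopper-Pearson 95% intervals for the response rates.

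**Other outputs.** SAP 10: "Demographic data and patient characteristics will be presented for the ENR". SAP 15: "All outputs for safety outcomes will be based on the ENR". SAP 9 says that all consenting patients will be accounted for.

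**The concern.** A set that needs only consent and a rule that also needs a completed injection cannot both define the primary analysis. The SAP defines two sets, screened and enrolled, so there is no completers set for SAP 7.2 to refer to.

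The rule conditions on something that happens after enrolment and may be caused by the pen. Protocol 5.6 lists failure to inject, partial injection and high operating force among the foreseeable device problems. In an ease-of-use study, a person who could not finish because of the pen may well answer below 6 (agree). Discarding that answer raises the agree/strongly agree proportion and its lower confidence bound, and protocol 10.2 and SAP 6.1 tie the intended claims to that bound.

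Completion is not defined either. The Instructions for Use foresee a participant who lifts the pen early and may not have delivered the full dose. Neither document says whether that counts as a completed simulated injection, so the decision could be taken with the answers in view.

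**Working it through.** **1. The plan's own figure.** The planned number with full data is 51 (SAP 6.1), with an assumed agreement of 95% (protocol synopsis, Sample Size). The margin is redacted. The usual precision formula is n = z²p(1 − p)/m². With z = 1.96, p = 0.95 and an assumed m = 0.06, n = 3.8416 × 0.0475 / 0.0036 = 50.69, rounded up to 51. Assumed margins of 5.5% and 6.5% give 61 and 44. So 51 is consistent with a 6-point margin, but this is a consistency check and not a reproduction. Nothing below depends on it.

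**2. What the exclusion adds to SAP 7.1.** Take a participant who is judged not to have completed the injection.

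- *No answer to the item.* SAP 7.1 already leaves this person out of the denominator, so SAP 7.2 changes neither the proportion nor the interval.
- *An answer to the item.* The ENR with SAP 7.1 keeps the answer; SAP 7.2 discards it.

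Only the second case matters for the primary proportion.

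**3. Can the second case occur?** Protocol 9.2.6 gives the questionnaire after the simulated injection. It neither requires completion nor says that a non-completer receives the form. Protocol and SAP give no expected count of non-completers. About 56 enrolled and 51 planned to complete leaves room for 5, but that gap also covers withdrawals and participants found ineligible after consent, who would have no answers.

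**4. Size, under assumed counts.** 95% of 51 is 48.45, so 48 and 49 agreeing bracket the plan. The two-sided 95% Clopper-Pearson lower bound for x of n is the 0.025 quantile of Beta(x, n − x + 1).

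| Answers counted | 49 agree: proportion (lower bound) | 48 agree: proportion (lower bound) |
|---|---|---|
| 51 completers only | 49/51 = 96.08% (86.54%) | 48/51 = 94.12% (83.76%) |
| plus one answer below 6 | 49/52 = 94.23% (84.05%) | 48/52 = 92.31% (81.46%) |
| plus two answers below 6 | 49/53 = 92.45% (81.79%) | 48/53 = 90.57% (79.34%) |
| plus one answer of 6 or 7 | 50/52 = 96.15% (86.79%) | 49/52 = 94.23% (84.05%) |

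From unrounded values, each added answer below 6 lowers the proportion by 1.85 then 1.78 points (49 agreeing), or 1.81 then 1.74 (48 agreeing). The lower bound falls by 2.49 then 2.26 points, or 2.30 then 2.12. One added answer of 6 or 7 raises the bound by 86.79 − 86.54 = 0.25 or 84.05 − 83.76 = 0.29 points.

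**5. SAP against protocol.** The condition in protocol 10.5 can mean that missing either the injection or the questionnaire excludes a participant, or that only missing both does. On the second reading, SAP 7.2 widens the exclusion without declaring it. On either reading, 10.5 already conflicts with 10.3.1, so the SAP did not create the conflict.

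**The case against.** The strongest reply is that the harm needs people whom the documents never show: someone judged not to have completed the injection, who was still given the questionnaire and answered below 6. That stands, and it limits the point to a possible effect.

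Several stronger readings are tempting and are not supported:

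- *An early lift, or a self-injection stopped by staff, is a non-completion.* The Instructions for Use say only that the full dose may not have been given. Protocol 5.7 says that staff stop the self-injection, not that the participant cannot then inject the pad. Some other pen failures lead to a replacement pen.
- *The questions on dose completion (5 and 12) show bias in the claim.* SAP 14.1.1 makes Questions 9 and 11 primary, and the sample-size text concerns overall ease and confidence. Questions 5 and 12 would be affected, but only as other variables.
- *Non-completers vanish from the demographic and safety tables.* SAP 7.2 taken alone could be read so, because it does not limit which analysis it means. The specific statements in SAP 9, 10 and 15 most naturally govern. A clarifying phrase is enough.

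It can also be argued that restricting to people who injected is sensible for questions about injecting. That is a fair secondary view, and a completers-only analysis provides it. It does not justify an undefined exclusion that contradicts the named primary set and is not needed to handle missing answers.

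**Conclusion.** The contradiction is certain from the text, and it should be resolved before database lock. Its effect on the result is conditional. It is zero if no participant judged a non-completer answers, and close to nil if those who answer choose 6 or 7. For each discarded answer below 6 on Question 9 or 11, it is 1.7 to 1.8 points on the proportion and 2.1 to 2.5 points on the lower bound. These sizes assume 48 or 49 agreeing among 51 completers and one or two such answers.

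A reader might infer that the rule will inflate the primary result or carry the lower bound over the claim threshold. The documents support neither: they do not show that such answers will exist, and the threshold is redacted.

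**What to change.** 1. Delete the injection-completion exclusion from SAP 7.2. Each item's primary denominator is then every ENR participant who answered that item (ENR with SAP 7.1, no imputation). No new population is needed.
2. Define a completed simulated injection for analysis purposes before database lock, and give the completers-only result as a sensitivity analysis.
3. Add a phrase that disposition, demographic and safety outputs stay on the full ENR, as SAP 9, 10 and 15 already say.
4. Record the reconciliation with protocol 10.5 in SAP 3.3, and align 10.5 with 10.3.1 at the next amendment, which needs IRB approval (protocol 13.2).
5. This does not recover participants who never receive the questionnaire. Report their number and the recorded discontinuation reasons from the SAP 9 disposition data.

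The cost is a few lines of SAP text, one extra table and, later, a protocol text change. The downside is a possibly slightly less favourable proportion.

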7.3 Examination of Subgroups

Subgroup analyses will be performed descriptively without comparisons between subgroups. The following subgroup analyses will be performed for this study:

- Injection experience (Yes, No) as defined in Section 10.

Document: ELI_LILLY_JAB94256_Auto_inj_SAP_v1.0_03JUN2024

Author: PPD

Version: 2.0

Version date: 16Jul2024

- Literacy (Limited literacy, Normal literacy) as defined in Section 10.
- Any comorbidity that involves joints (Yes, No) as defined in Section 11.

If there are fewer than 5 patients in a given subgroup, that data will not be summarized. Given that the sample size calculations did not consider subgrouping, the analyses will be exploratory in nature.

7.4 Randomization Schedule

No randomization will be performed for this study.

8. OUTPUT PRESENTATIONS

TLFs shells will be developed by IQVIA RWS Biostatistics using the standard processes. The format and content of the statistical analysis is illustrated in the TLF shells provided with this SAP.

9. DISPOSITION AND WITHDRAWALS

All patients who provide informed consent will be accounted for in this study. Subject disposition will be summarized in terms of number and percentages (n, %) for the below variables (see [Section 7.1](#) for more details). Unless specified otherwise, percentages will be calculated using the number of patients from ENR as denominator.

- Patients in SCR.
- Patients in ENR.
- Patients not meeting eligibility criteria.
- Patients who completed the study.
- Patients who discontinued the study.
- Reason for study discontinuation.
 - Adverse Event or Serious Adverse Event
 - Noncompliance with Protocol
 - Withdraw consent
 - Screen Failure
 - Other

Document: ELI_LILLY_JAB94256_Auto_inj_SAP_v1.0_03JUN2024

Author: PPD

Version: 2.0

Version date: 16Jul2024

For the variables “Patients in ENR” and “Patients not meeting eligibility criteria”, percentages are calculated based on SCR as denominator.

A listing will also be provided for the above disposition data.

10. DEMOGRAPHIC AND OTHER PATIENT CHARACTERISTICS

Demographic data and patient characteristics will be presented for the ENR. No statistical testing will be carried out for demographic or patient characteristics. The following demographic characteristics will be presented as described in [Section 7.1](#):

- Age at enrollment (years)
- Sex (Male, Female)
- Race (American Indian or Alaska Native, Asian, Black or African American, Native Hawaiian or Pacific Islander, White, Other, Multiple, Refused to answer)
- Ethnicity (Hispanic, Non-hispanic)
- Education (Less than High School, Completed High School/GED, Some College/Technical School, Graduated College/Technical School or more, refused to answer)
- Employment status (Employed Full-Time, Employed Part-Time, Unemployed, Student, Retired, Other, refused to answer)
- Total annual household income (\$0 to \$14,999, \$15,000 to \$24,999, \$25,000 to \$34,999, \$35,000 to \$44,999, \$45,000 to \$64,999, \$65,000 to \$74,999, \$75,000 or more, refused to answer)

A listing will also be provided for the above demographic characteristics.

Descriptive statistics (see [Section 7.1](#)) will be provided for the following patient characteristics:

Injection Experience:

- Number of subjects with any previous injection experience (Yes, No)
- Number and percentage of injection tool used (pre-filled syringe (PFS), Vial/Syringe, Other)

- Number and percentage of previous injection experience (Perform injections frequently on self, perform injections frequently on others, perform injections rarely on self, perform injections rarely on others)

A listing of injection experience will be provided for each term as collected in the eCRF, including the data listed above, the drug and/or device used for injection, and the last time they performed an injection.

Pregnancy:

- Number and percentage of participants who are individuals not of childbearing potential (INOCBP) (Yes, No)
- Number and percentage of Reason for being INOCBP (Surgically sterilized, Tubal Ligation, not capable of producing ova or embryo due to congenital anomaly)
- Number and percentage of pregnancy test completed (Yes, No)
 - Number and percentage of reason for pregnancy test not performed (Refused, unable to urinate, other)
 - Participants who read Instructions for Use (Yes, No)
 - Participant given the opportunity to have their questions about the injection simulation process answered (Yes, No)
 - Injection simulation observation for correct demonstration of below tasks:
 - Task 1: Uncap the pen (Yes, No, Not assessed).
 - Task 2: Place and unlock (Yes, No, Not assessed).
 - Task 3: Press and hold for 15 seconds (Yes, No, Not assessed). Note that "Press and hold for 15 seconds" means that you should either press and hold for 15 seconds or wait for the second click as outlined in task 3 of the Instructions for Use (IFU).

11. MEDICAL HISTORY

A brief medical history will be conducted to gather information about the approximate date of participants' AD diagnosis and any previous or current AD treatments. Data will be captured during

Document: ELI_LILLY_JAB94256_Auto_inj_SAP_v1.0_03JUN2024

Author: PPD

Version: 2.0

Version date: 16Jul2024

the enrollment visit and will be presented for the ENR. Medical History and Comorbidities will be coded using the Medical Dictionary for Regulatory Activities (MedDRA). The MedDRA version used for a given output will be added in the footnote.

The following will be presented:

- Number and percentage of participants who normally wear corrective lenses, contacts, or glasses to read? (Yes, No)
- Number and percentage of participants who have any difficulty, even with glasses, reading small print, such as labels on medicine bottles, a telephone book, or food label? (No difficulty, A little difficulty, A moderate amount of difficulty, A great deal of difficulty, Unable to perform the activity, Not applicable).
- Number and percentage of any of the following conditions:
 - Osteoarthritis
 - Rheumatoid Arthritis
 - Carpal Tunnel Syndrome
 - Neuropathy
 - Other
- Number and percentage of, how difficult was it for you during the last 48 hours to unlock your door with a key because of finger joint problems? (Not at all difficult, A little difficult, Moderately difficult, Very difficult, I am unable to perform this activity, Not applicable).
- Number and percentage of, how difficult was it for you during the last 48 hours to zip up or unzip a zipper because of finger joint problems? (Not at all difficult, A little difficult, Moderately difficult, Very difficult, I am unable to perform this activity, Not applicable).

A listing by patient including each term as collected in the eCRF.

12. CONCOMITANT MEDICATION

A listing by patient including each medication term, indication, start and end date, ongoing condition (Yes/No), infected body system, dose, unit, dose form, route, and frequency will be included as collected in the eCRF.

Document: ELI_LILLY_JAB94256_Auto_inj_SAP_v1.0_03JUN2024

Author: PPD

Version: 2.0

Version date: 16Jul2024

13. STUDY MEDICATION EXPOSURE

No study medication will be given in this study.

14. PRIMARY OUTCOME

14.1 Primary Endpoint

The primary endpoints are the ease of use and confidence of lebrikizumab administrations via a prefilled pen using the modified Subcutaneous Administration Assessment Questionnaire (mSQAAQ) following training on the pen.

14.1.1 Primary Variables

The SQAAQ is an innovative, 12-item, self-administered questionnaire designed to evaluate the user-friendliness of the device and the patient's confidence during the administration of a subcutaneous injection of a medication. In this study, evaluation of the subject's experience will be based on the mSQAAQ, a self-administered questionnaire that assesses the ease of use and confidence in using the lebrikizumab pen. This tool is comprised of 10 questions (of which 2 questions were removed in the eCRF). Responses are scored on a 7-point Likert scale ranging from 'strongly disagree' to 'strongly agree' as follows:

1 - Strongly disagree

2 - Disagree

3 - Slightly Disagree

4 - Neither agree nor disagree

5 - Slightly agree

6 – Agree*

7 - Strongly agree*

*A combined response of "Agree" or "Strongly agree" will also be presented for all questions.

The following are the questions were removed in the eCRF:

- Question 6: Easy to store device in refrigerator

Document: ELI_LILLY_JAB94256_Auto_inj_SAP_v1.0_03JUN2024

Author: PPD

Version: 2.0

Version date: 16Jul2024

- Question 10: Device is stable against skin during injection

The primary variables are the results reported for each element of the mSQAAQ, which are as follows:

- Question 9: Overall, easy to use
- Question 11: I am confident in my ability to use the device

The other variables are the results reported for each element of the mSQAAQ, which are as follows:

- Question 1: Easy for me to learn how to use
- Question 2: Easy for me to unlock
- Question 3: Easy to hold in my hand when I inject my dose
- Question 4: Easy to inject my dose
- Question 5: Easy to know that my dose is complete
- Question 7: Easy to remove needle shield/cover
- Question 8: Easy to pick up
- Question 12: I am confident my dose is complete

Number, percentage, and 95% confidence interval of partial responders will also provide, overall.

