### **Sample Size**

The planned analysis population for this descriptive study is 51 participants. Sample size was calculated based on the following assumptions: CC1 95% of the participants will respond “agreed” or “strongly agreed” to each individual mSQAAQ  question, with associated 95% confidence intervals. No comparative analyses are planned for this study.

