3.3 Changes to Analysis from Protocol

No changes from protocol.

Document: ELI_LILLY_JAB94256_Auto_inj_SAP_v1.0_03JUN2024

Author: PPD

Version: 2.0

Version date: 16Jul2024

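### Does it matter that the SAP lists two mSQAAQ items as primary when the protocol ranks none of the ten?

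*SAP*

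**What the plan says.** **Protocol.** Section 10.3.1 reads "The primary outcome reported from each individual question will be the proportion of participants responding" in the top two categories. It names no subset of questions. The synopsis likewise analyses the ten questions one by one, and its sample size paragraph applies the 95% assumption "to each individual mSQAAQ" question. Protocol 10.2 is narrower. It bases the sizing, and the lower confidence bound wanted for the intended claims, on two statements: that the device is easy to use and that participants are confident they can use it.

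**SAP.** Section 6.1 repeats protocol 10.2. Section 14.1.1 introduces its first list with "The primary variables are the results reported for each element of the mSQAAQ, which are as follows" and gives Questions 9 and 11. It introduces a second list with "The other variables are the results reported for each element of the mSQAAQ, which are as follows" and gives the remaining eight. A footnote to the response scale says that the combined agree/strongly agree response "will also be presented for all questions". Section 14.1.2 says "Each element will be summarized using descriptive statistics" and refers to section 7.1, where the 95% interval "for the response rates will be calculated using Clopper-Pearson method". Section 3.3 declares "No changes from protocol".

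**The concern.** Three things look wrong.

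- **Items.** The protocol gives every question the same standing. The SAP promotes two and demotes eight, and its lead-in says each element while listing two.
- **Measure.** The protocol names the top-two-category proportion as the primary outcome. In the SAP that proportion appears in a footnote as something also shown, and the primary variable is only described as the results reported. A seven-point item could be summarised by a mean, a median, seven percentages or one proportion.
- **Record.** The section meant to list departures from the protocol lists none.

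In a confirmatory trial this would be serious. Narrowing the primary set in a later document, without recording it, leaves room to headline whichever items did best, and it changes what any multiplicity control covers. Here the worry would be that a reader of the report could not trace the headline items to the plan.

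**Working it through.** **1. Count the items (SAP 14.1.1).** The parent questionnaire has 12 questions, and Questions 6 and 10 were removed: 12 − 2 = 10. Primary list: {9, 11}, 2 items. Other list: {1, 2, 3, 4, 5, 7, 8, 12}, 8 items. The lists do not overlap, and 2 + 8 = 10, so every item is placed. Read strictly against protocol 10.3.1, 8 of 10 items change label.

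**2. Does the label change the sample size?** The plan's figure is 51, at an assumed proportion of 95%. The margin of error is redacted, so it has to be assumed. The usual precision formula for one proportion is n = z²p(1 − p)/m², with z = 1.96 and p = 0.95:

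| Assumed margin m | n |
|---|---|
| 5% | 72.99, rounded up to 73 |
| 6% | 50.69, rounded up to 51 |
| 7% | 37.24, rounded up to 38 |
| 8% | 28.51, rounded up to 29 |

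A 6-point margin reproduces 51, although the redaction prevents confirmation. The formula concerns one item at a time and contains no term for the number of items. Two primary items or ten give the same n.

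**3. Does the label change an estimate or interval?** For each item the estimate is x/n, where x counts answers of 6 or 7 and n counts non-missing answers (SAP 7.1). The Clopper-Pearson limits depend only on x and n. The footnote in 14.1.1 provides the proportion for all ten items. Both lists describe their contents as elements of the questionnaire, and 14.1.2 applies one rule to each element. The output is therefore the same under either label.

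**4. Does the SAP replace the primary measure?** It names no rival. The footnote hangs on response options 6 and 7, so its also most naturally means in addition to the seven separate categories. SAP 6.1 calls the agree/strongly agree proportion the response rate, and 7.1 gives the exact interval for response rates. Section 14.1.2 refers to 7.1, so the reference reaches the protocol's measure.

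**5. Where do Questions 9 and 11 come from?** Protocol 10.2 names ease of use and confidence in using the device. The study objective (protocol 6.4) names the same two concepts. Question 9 is the overall ease item and Question 11 the confidence-in-use item. The selection can be traced to protocol text and was not introduced by the SAP.

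**The case for a change.** The strongest case for acting is the lower bound. Protocol 10.2 and SAP 6.1 tie the study to intended claims that need a 95% lower limit above a redacted value. If that bound had to hold for every primary item, two items or ten would matter a good deal. Taking a true rate of 95%, 51 participants and independent items, the chance that all the lower limits clear an assumed threshold is:

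| Assumed threshold | Needed | One item | Two items | Ten items |
|---|---|---|---|---|
| 75% | 45/51 | 0.987 | 0.974 | 0.877 |
| 80% | 47/51 | 0.890 | 0.791 | 0.310 |
| 85% | 49/51 | 0.527 | 0.278 | 0.002 |

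The arithmetic is right, but it does not carry the point. In both documents the bound sits in the same paragraph as the ease and confidence statements, so its scope can be read from the text. The synopsis, which speaks of each question, gives a sizing assumption and no bound. The thresholds are assumed, and ten answers from one person about one injection will not be independent, which would narrow the gap between two items and ten.

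Three things do stand: the lead-in in 14.1.1 is inaccurate, protocol 10.3.1 and the synopsis rank no question, and SAP 3.3 could have recorded the ranking. The reply that 10.3.1 only says what is reported from a question, and not which questions rank first, is tenable but not the only reading. The table shells supplied with the SAP (section 8) may settle the presentation, but they are not among the documents reviewed.

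**Conclusion.** No change to the plan follows. The mismatch is a matter of labels: up to eight of ten items, one inaccurate lead-in and one unrecorded distinction. It alters no estimate, confidence interval, denominator or sample size. An analyst following the SAP as written will report the agree/strongly agree proportion for all ten items with an exact interval available, which is what protocol 10.3.1 asks for. The two headline items are those that protocol 10.2 had already tied to the claims. Rewording would relabel the results and add nothing to them.

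This rests on three features of the documents: the study is descriptive with no comparative analyses, the combined response is presented for every item, and the lower bound is read with the two statements beside it. If a test, a multiplicity procedure or a decision rule hung on the primary set, the same discrepancy would have to be corrected.
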